9 EFFICACY AND SAFETY ANALYSES

9.1 Overview of Analysis Methods

The statistical goal for the study is to evaluate the effects of sublingual buprenorphine (BUP; Subutex) combined with extended-release injectable naltrexone (NTRX; Vivitrol) in the treatment of comorbid PTSD and AUD. Although the analyses will use data collected from baseline through week 12, the primary hypothesis that the primary outcome differs between the treatment arm vs. placebo will be tested at Week 8. The analysis also will formally test treatment differences for the PTSD and AUD outcomes, independently. Primary and exploratory analyses will use model-based approaches that take advantage of the longitudinal structure of the outcome data to address missing data caused by patient loss to follow-up or nonresponse and take into

consideration correlated data collected across time. Additional analytic details are in the sections below.

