10.4.9 MULTIPLE COMPARISON/MULTIPLICITY

No adjustments for multiple comparisons are planned for the primary efficacy or safety outcomes. For the secondary outcomes, we will group by outcome domain and apply Benjamini-Hochberg (1995) false discovery rate correction to maintain the nominal alpha level of 0.05.

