3.1.2 Primary Efficacy Objectives

1. To evaluate the efficacy of BUP/NTRX in the treatment of comorbid PTSD and moderate-to-severe AUD based on a matrix outcome of response in terms of both PTSD and AUD outcomes over the 8-week study period.
2. Determine if percent of heavy drinking days (defined as >4 standard drinks/sessions for men and >3 standard drinks/sessions for women) as assessed by the Timeline Follow-Back (TLFB) are reduced for BUP/NTRX treatment over the 8-week study period.
3. Determine if PTSD symptoms, as measured by the change in the Clinician Administered PTSD Scale for DSM-5 (CAPS-5), are reduced for BUP/NTRX treatment over the 8-week study period.

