3.2.1 Primary Efficacy Outcomes

As mentioned above, the **primary outcome** is a matrix outcome of response in terms of both PTSD and AUD outcomes. The derivation of this measure will be a binary “yes/no” outcome. The PTSD outcome will be assessed using the CAPS-5 and be defined as “yes” if there is a decrease ≥ 10 points from baseline to week 8. The AUD outcome will be assessed using the TLFB and %HDD. The AUD outcome will be defined as “yes” if there is a reduction >1 -shift in World Health Organization (WHO) risk levels of alcohol use from baseline to week 8 (note: the look-back period will consist of 28 consecutive days).

As a complement to the primary outcome, we will also examine each of the components individually (CAPS-5 Total Symptom Severity Score and %HDD)

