7 STATISTICAL / ANALYTICAL ISSUES

7.1 General Rules

All statistical computations will be performed and data summaries will be created using SAS 9.4 or higher. If additional statistical packages are required, these will be discussed in the study report. For summaries of study data, categorical measures will be summarized in tables listing the frequency and the percentage of participants; continuous data will be summarized by presenting mean, standard deviation, median and range; and ordinal data will be summarized by only presenting median and range. Model-based analyses described in Section 9 will be used to obtain point estimates and associated confidence intervals for various measures as well as p-values for comparisons of data between treatment groups. Note: initial models will include the high dose treatment arm; however, if the model cannot converge due to the small number of participants randomized to this arm prior to removal from the study, then the model will only compare outcomes between the low dose and placebo treatments. P-values presented will be based on two-sided tests unless otherwise specified and generally only adjusted for randomization factors (study site, gender, and presence of concomitant antidepressants). Note: in the event a model cannot converge due to small sample sizes for a specific randomization factor, it will be removed from the model. For continuous outcomes, checks of normality will be performed and if required, transformations or non-parametric tests will be employed.

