7.7 Multiple Comparisons and Multiplicity

One single primary formal hypothesis test is planned for this study at the 0.05 level of significance, which is the comparison of the SL-BUP + XR-NTX treatment group vs. placebo for the primary outcome at the primary timepoint (Week 8). Additionally, regardless of significance of the primary outcome, statistical significance of the secondary outcomes will be assessed, with adjustment for multiple comparisons using the Benjamini-Hochberg false discovery rate correction to maintain the nominal alpha level of 0.05 (Benjamini & Hochberg, 1995). Primary and secondary hypothesis tests resulting in nonsignificant p-values will be interpreted as inconclusive. All other treatment group comparisons will be considered descriptive in nature with no adjustment for multiple comparisons, and all confidence intervals will be generated using 95% bounds.

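### The SAP contradicts itself on which tests are confirmatory: 7.7 allows one formal primary test, other sections make CAPS-5 and %HDD primary and formally tested, and the only multiplicity correction covers outcomes the SAP no longer defines

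*SAP*

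**What the plan says.** SAP 7.7 is the multiplicity section. It states: "One single primary formal hypothesis test is planned for this study at the 0.05 level of significance", and identifies that test as active versus placebo on the primary outcome at Week 8. It adds that, whatever the primary result, "statistical significance of the secondary outcomes will be assessed, with adjustment for multiple comparisons using the Benjamini-Hochberg" method. Non-significant primary and secondary tests are to be read as inconclusive, and all remaining group comparisons are descriptive and unadjusted. SAP 3.2.1 fits this, naming the composite as the primary outcome and saying of the rest: "As a complement to the primary outcome, we will also examine each of the components individually".

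Other parts of the SAP say something different:

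- **3.1.2** numbers three Primary Efficacy Objectives: the composite, then one beginning "Determine if percent of heavy drinking days", then change in CAPS-5.
- **9.1** follows the primary hypothesis with "The analysis also will formally test treatment differences for the PTSD and AUD outcomes, independently".
- **9.2** places the composite, %HDD and the CAPS-5 total score together in the primary block of its outcome table.
- **9.3.1 and 9.3.2**, inside the primary efficacy methods, give CAPS-5 and %HDD each a confidence interval and a p-value, with no adjustment.

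Protocol 10.4.9 states: "No adjustments for multiple comparisons are planned for the primary efficacy or safety outcomes". For secondary outcomes it groups by outcome domain and applies Benjamini-Hochberg.

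**The concern.** A comparison cannot be both descriptive and formally tested, and no passage says which statement governs. Three rules for the components could be defended from the text: descriptive (7.7), formal primary tests at an unadjusted 0.05 (3.1.2, 9.1, 9.2 and protocol 10.4.9), or the secondary outcomes that 7.7 has in mind (which contradicts their primary label). The choice could be made after the results are known.

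The safeguard that 7.7 does offer is empty within the SAP. Fear-potentiated startle was moved from secondary to exploratory in version 2.0 and taken out in version 3.0. Sections 3.2 and 9.2 now contain only primary, exploratory, safety and (in 9.2) adherence outcomes. The one remaining secondary label in the efficacy methods, in 9.3, is attached to timepoints. The protocol still lists psychophysiological secondary outcomes (4.2.2, 10.4.3), but this SAP does not analyse them.

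This matters because a null composite beside one nominally significant component is a realistic result. The protocol's own table (10.5) gives the composite power of 0.795 at 5/45 versus 17/45 and 0.560 at 5/45 versus 14/45. The hypothesis requires response in both disorders, and XR-NTX is already approved for alcohol dependence (protocol 2.3.2). A result on %HDD alone, reported as primary, would not support the comorbid claim.

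**Working it through.** **Inputs from the documents**

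- Level 0.05 for the composite (SAP 7.7).
- Sidedness: "P-values presented will be based on two-sided tests unless otherwise specified" (SAP 7.1).
- Two further tests, CAPS-5 and %HDD (SAP 9.1, 9.3.1, 9.3.2).
- 45 per arm, and about 30% attrition (SAP 6).

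The documents give no correlation between the outcomes. All correlations below are assumptions.

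**1. The plan's own figure.** With the composite as the only confirmatory test, the error is 1 − 0.95 = 0.05, as 7.7 states.

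**2. Any of three at 0.05, independent, all nulls true.** 1 − 0.95³ = 1 − 0.857375 = 0.1426, or 14.3%.

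**3. Correlated tests.** Trivariate normal test statistics, each at exactly 5% two-sided:

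| Component correlation | Composite–component correlation | Any of three, two-sided | Any of three, favouring drug |
|---|---|---|---|
| 0 | 0.40 | 13.5% | 6.8% |
| 0.2 | 0.45 | 13.2% | 6.6% |
| 0.3 | 0.50 | 12.8% | 6.4% |
| 0.5 | 0.50–0.60 | 12.0–12.6% | 6.0–6.3% |
| 0.7 | 0.55–0.65 | 11.2–11.8% | 5.6–5.9% |
| 0.9 | 0.70 | 9.9% | 4.9% |

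The nominal rate in the drug's favour for one test is 2.5%. For three independent tests it is 1 − 0.975³ = 7.3%.

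**4. Data-level check.** Change scores were simulated as bivariate normal, with the composite defined as both changes passing a threshold, at 45 per arm. At a null composite rate of 11%, any-of-three was 14.7% at correlation 0, 13.3% at 0.5 and 11.4% at 0.9. At a null rate of 25% it was 13.7%, 12.4% and 10.2%. The chi-square test used for the composite in this check ran at 5.1–6.1%, which slightly raises these figures. With 32 per arm (45 × 0.7 = 31.5) the range was 10.1–14.1%.

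**5. After the fix.** Benjamini-Hochberg on two p-values rejects both if the larger is at most 0.05, and otherwise rejects the smaller if it is at most 0.025. For two independent nulls, the chance of any rejection is 0.05² + (1 − 0.975²) − (0.05² − 0.025²) = 0.0025 + 0.049375 − 0.001875 = 0.05. With an independent composite at 0.05, any-of-three is 1 − 0.95 × 0.95 = 0.0975, or 9.8%. At component correlations of 0.2–0.7 it is about 8–9%. The composite alone remains at 5%.

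**The case against.** The strongest reply is that 7.7 governs multiplicity and is clear: one test, at one timepoint, with other comparisons descriptive. SAP 3.2.1, 9.3 and the sentence in 9.1 just before the quoted one all speak of a single primary outcome or hypothesis, and protocol 4.2.1, 10.2 and 10.4.2 call the components a complement. Since 7.7 treats a non-significant primary test as inconclusive, calling a null composite a primary success would breach the SAP. The trial is also a Phase II proof of concept.

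Most of this stands. A reader might infer that the trial's primary type I error is 12–14% rather than 5%. The documents do not support that. It needs a rule that a win on any of the three counts, which no passage states. It also counts false results in either direction, and it depends on correlations that the documents do not supply.

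A reader might also infer that the secondary family has disappeared altogether. It has gone from the SAP but not from the protocol.

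The reply does not remove the contradiction. 7.7 does not say that it overrides 3.1.2, 9.1 or 9.2, and its Benjamini-Hochberg sentence cannot be carried out with the outcomes that the SAP now lists.

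**Conclusion.** The inconsistency is real and visible in the text: one confirmatory test in 7.7, three outcomes labelled primary elsewhere, two of them formally tested without adjustment, and a correction rule with nothing to act on.

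The error of the declared primary hypothesis is 5% and is not in question. The exposure is conditional. If any one of the three could carry a primary claim, the two-sided chance of at least one false positive would be 14.3% under independence and about 10–14% for assumed component correlations of 0 to 0.9. False results favouring the drug would be about half of that.

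Severity: should-fix, because 7.7 does name the primary test. Label: wrong as written, because the multiplicity rule cannot be applied to the outcomes as the SAP classifies them.

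**What to change.** Before the data are locked and unmasked (protocol 10.1 requires the SAP to be final by then):

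1. Keep the composite at Week 8 as the only primary test, two-sided at 0.05.
2. In SAP 3.1.2, 9.1 and 9.2, relabel Week 8 CAPS-5 and Week 8 %HDD as the two secondary outcomes.
3. In 7.7, name these two p-values as one Benjamini-Hochberg family. Align protocol 10.4.9 so that they are not split by outcome domain. A PTSD family and an AUD family of one member each would receive no correction.
4. State that a non-significant composite cannot be reported as a primary success, whatever the components show.

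**Cost.** This is wording only, with no new data, model or sample size. The components face a slightly stricter threshold: 0.025 when only one of them is below 0.05. Because 7.7 tests the secondaries regardless of the primary result, the chance of at least one false positive among the three would still be about 9.8% if independent. Only the composite would carry the primary claim, at 5%.

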9.2 Efficacy and Safety Outcome Variables

Variable	Type	Definition														
Primary Outcomes																
Composite AUD + PTSD outcome	Binary (Yes/No)	
A positive response is defined as a decrease from baseline of at least 10 points on the CAPS-5 score (Schnurr et al., 2022) and a reduction of at least 1 risk level of alcohol use, as defined by WHO, at week 8. AUD data is collected on the TLFB, a semi-structured interview that uses a calendar prompt and other memory aids to facilitate accurate recall of the numbers of drinks consumed each day during a given target period (Sobell et al., 1996). The definition of WHO risk drinking levels are defined by Knox et al. (2018), and displayed in the below table
 
  
 Wave 1 WHO risk drinking level	Definition of each level, in grams (US standard drinks)	
   
 Very high	>100 g (>7.1 drinks) for men;	
 
 >60 g (>4.3 drinks) for women	
 
 High	60–100 g (4.3–7.1 drinks) for men;	
 
 40–60 g (2.9–4.3 drinks) for women	
 
 Moderate	40–60 g (2.9–4.3 drinks) for men;	
 
 20–40 g (1.4–2.9 drinks) for women	
 
 Low	1–40 g (<2.9 drinks) for men;	
 
 1–20 g (<1.4 drinks) for women	
  
	Wave 1 WHO risk drinking level	Definition of each level, in grams (US standard drinks)	Very high	>100 g (>7.1 drinks) for men;	>60 g (>4.3 drinks) for women	High	60–100 g (4.3–7.1 drinks) for men;	40–60 g (2.9–4.3 drinks) for women	Moderate	40–60 g (2.9–4.3 drinks) for men;	20–40 g (1.4–2.9 drinks) for women	Low	1–40 g (<2.9 drinks) for men;	1–20 g (<1.4 drinks) for women
Wave 1 WHO risk drinking level	Definition of each level, in grams (US standard drinks)															
Very high	>100 g (>7.1 drinks) for men;															
	>60 g (>4.3 drinks) for women															
High	60–100 g (4.3–7.1 drinks) for men;															
	40–60 g (2.9–4.3 drinks) for women															
Moderate	40–60 g (2.9–4.3 drinks) for men;															
	20–40 g (1.4–2.9 drinks) for women															
Low	1–40 g (<2.9 drinks) for men;															
	1–20 g (<1.4 drinks) for women															

Variable	Type	Definition
		
The TLFB assessment is given at screening, baseline, and weeks 1, 2, 4, 6, 8, 10, and 12. The screening measurement uses a 90-day recall period whereas the subsequent (post treatment follow up) measurements use a recall period of “since the last measurement.” The baseline WHO risk level will be derived from TLFB data collected at both the screening and baseline visit. The look-back period to define the WHO risk level will be conducted over 28 consecutive days and based on the average number of reported standard drinks during those 28 consecutive days. Each derived outcome measure for a specific timepoint will be based on the baseline visit date. In the event 28 consecutive days are not captured for the full look-back period, participant data will be excluded from analyses in the event the number of total days included in look-back period is less than one standard deviation of the entire population.

Percent Heavy Drinking Days (%HDD)	Continuous (range between 0 and 100)	
Percent Heavy Drinking Days (%HDD) is measured via the Timeline Follow Back instrument (Sobell et al., 1996). The screening (baseline) measurement uses a 90-day recall period whereas the subsequent (post treatment follow up) measurements use a recall period of “since the last measurement.” Baseline %HDD will be derived from TLFB data collected at both the screening and baseline visit. The look-back period to define %HDD will be conducted over 28 consecutive days and based on the number of heavy drinking days reported during this time period. Each derived outcome measure for a specific timepoint will be based on the baseline visit date. In the event 28 consecutive days are not captured for the full look-back period, participant data will be excluded from analyses in the event the number of total days included in look-back period is less than one standard deviation of the entire population.
 
A heavy drinking day is defined as follows:
 
>4 standard drinks/sessions for men and >3 standard drinks/sessions for women

Variable	Type	Definition
CAPS-5 Total Symptom Severity Score	Continuous (range between 0 and 80)	CAPS-5 total symptom severity score is measured via the Clinician-Administered PTSD Scale For DSM-5 (CAPS-5). The score is calculated by summing severity scores for the 20 DSM-5 PTSD symptoms (Weathers et al., 2013), with a higher score indicating worse PTSD symptoms.
Exploratory Outcomes		
PCL-5 Score	Continuous (range between 0 and 80)	The PCL-5 is a 20-item self-report measure that assesses the 20 DSM-5 symptoms of PTSD. Its purposes include screening for PTSD and/or provisional diagnosis, and monitoring symptom change before, during, and after treatment. A total symptom severity score ranging from 0 to 80 is possible (Weathers et al., 2013). The score is calculated by summing each of the 20 DSM-5 PTSD questions, with a higher score indicating worse PTSD symptoms.
PHQ-9 Score	Continuous (range between 0 and 27)	Depression symptoms will be assessed using the validated PHQ-9 (Kroenke, Spitzer, & Williams, 2001) in support of exploratory analyses. The PHQ-9 was developed as a short form of the full Patient Health Questionnaire (which was a self-administered version of the PRIME-MD instrument). Severity scores range from 0 to 27, with a score of 5 to 9 representing mild depression, a score of 10 to 14 representing moderate depression, and a score of 15 or greater representing a severe level of depression (Kroenke et al., 2001).
VR-12 Scores (physical and mental health summaries)	Continuous (T-score with a mean of 50 and standard deviation of 10)	The VR-12© was developed from the Veterans RAND 36 Item Health Survey (VR-36©; formerly called the Veterans SF-36), which was adapted from the RAND 36-Item Health Survey (RAND 36 version 1.0) at the RAND Corporation and the Medical Outcomes Study. The twelve items provide an estimate for eight domains of functional health and well-being: physical functioning, role-physical, bodily pain, general health, vitality, social functioning, role-emotional, and mental health. Together, the first four domains constitute a Physical Health

Variable	Type	Definition
		summary (PCS) measure, and the second 4 constitute a Mental Health summary (MCS) measure (Ware, Kosinski, & Keller, 1996). PCS and MCS scores are derived using an algorithm that is referenced to a metric centered at 50.0 using the 2000–2002 US Medical Expenditure Panel Survey population.
Phosphatidyl ethanol (PEth)	Continuous (range between 0 and >210 ng/mL)	
Phosphatidyl ethanol (PEth) are a series of abnormal phospholipids located in the cell membrane and formed in the presence of ethanol and phospholipase D. PEth serves as a biomarker of alcohol ingestion in the past 2-3 weeks using liquid chromatography tandem mass spectrometric assessment of human blood (whole or dried spots). PEth in blood is often used as a marker of chronic alcohol use and was collected at baseline and weeks 8 and 12.
 
At the present time, the international scientific community has not yet established a cut-off value for PEth concentration in blood to be used for differentiating an acceptable social ethanol intake (<40 g for males and <20 g for females, according to the WHO parameters), from an at-risk-alcohol-use (40–60 g/die) and chronic excessive drinking behavior (>60 g/die). However, per LabCorp, PEth levels in excess of 20 ng/mL are considered evidence of moderate to heavy ethanol consumption.

Safety Outcomes		
Adverse Events	Counts and proportions	Total number and proportion of treatment emergent adverse events. Comparison of AE rates by treatment group will also be stratified by type and severity.
Withdrawals due to Adverse Events	Proportion	Proportions of individuals by treatment group who withdrew from the study due to adverse events
Adherence and Retention Outcomes		

Variable	Type	Definition
Serum Buprenorphine and Norbuprenorphine	Continuous	
Buprenorphine and its metabolite norbuprenorphine are assayed using liquid chromatography tandem mass spectrometry by a commercial laboratory. Sample results are available via the commercial laboratory portal using a study specific username/password combination and the unique participant code/requisition number.
 
To assess medication adherence, blood samples collected at study weeks 8 and 12 will be tested for buprenorphine and its metabolite, norbuprenorphine, using quantitative assessments.

Pill Count	Count and proportion	
A dosing log case report form (CRF) is completed weekly (or since the last in-person visit) for each participant. The number of completed NTX injections received (at baseline, week 4, and week 8) is recorded, as well as the number of missed SL-BUP pills per week. For each medication (NTX and SL-BUP), the proportion of subjects who missed any treatment will be derived, as well as the total number of missed injections or pills, per participant.

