5.4.2 HANDLING OF PARTICIPANT WITHDRAWALS OR TERMINATION

If an early exit occurs, the reason(s) for early termination is documented and all Week 12 procedures are conducted. A post-study phone call or visit is scheduled with the research team to ensure that the participant has made or scheduled the appropriate follow-up appointments and to address any clinical problems or AEs that may have occurred.

Participants may stop study medication but are encouraged to remain in the study for follow-up assessments. In this case, the participant may attend assessments for data collection or consent to allow for continued follow-up through chart review. If a participant withdraws from the interventional portion of a study and does not consent to continued follow-up of associated clinical outcome information, then the investigators will not access the participant's medical record or make future contact with the participant. If a study participant withdraws consent for study participation, then the participant is excluded from all future study procedures and treatments. No additional study data is collected from the participant after consent has been withdrawn.

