7.3.4 FOLLOW-UP VISITS

Assessments occur at screening, baseline, and post-randomization Weeks 1, 2, 4, 6, 8, 10, and 12. There is a visit window of +/- 7 days for follow-up visits.

The investigators and CRCs provide ongoing reinforcement of the patients' commitment to long-term follow-up. The study medication providers emphasize the need to properly adhere to prescribed treatments or to call to revise the treatments if side effects occur or therapeutic effects are lost.

Adherence to SL-BUP medication is confirmed by pill count. Concomitant medications are updated at each of these visits.

If participants experience side effects that cannot be managed by adjustments in the timing of the medication (i.e., taking at bedtime, etc.), they may have their medication titration either held or the medication dosing may be decreased (i.e., less frequent).

The CRC makes a telephone (t) contact with the participant between face-to-face visits to remind the participant of the next office visit and to check on adherence to the study medication and if there have been any serious adverse events.

*Psychophysiological assessments are optional to not be a barrier to enrollment or randomization.

The one-day psychophysiological assessment is repeated at Week 2.

The two-day psychophysiological assessment is repeated at Week 8.

At Week 8, the participant remains on the assigned treatment and dose from Week 8 to Week 12.

While every attempt is made to retain the participant in the study on medication for the full 12 weeks, the participant may discontinue medication at any point and remain in the study for assessments through Week 12.

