7.3.6 EARLY TERMINATION VISIT

If a participant exits prior to Week 8, all procedures for Week 8 are completed. If the participant exits after Week 8 but prior to Week 12, all Week-12 procedures are completed.

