7.9 Assessment Windows

All screening assessments will be performed prior to Day 0 (study baseline/admission). Screening will take place over 1 to 14 days and include the study instruments listed in the table above (section 4.5). Most screening assessments are repeated at Day 0 if occurring more than one-month post screening. The most recent data collected during the screening/baseline period will be used for summarizing and analyzing baseline data.

Participants will visit their respective site to complete study procedures at weeks 1, 2, 4, 6, 8, 10, and 12. The visit windows for these in-person visits is +/- 7-days. It is important to confirm

appointment with subjects at each visit, so that if adjustments need to be made so that the subject does not run out of medication between the scheduled in-person visits. The CRC will make a telephone contact with the participant between face-to-face visits to remind the participant of the next office visit and to check on adherence to the study medication and if there have been any adverse events. While every attempt is made to retain the participant in the study on medication for the full 12 weeks, the participant may discontinue medication at any point and remain in the study for assessments through week 12. Out-of-window visits or assessments must be reported as protocol deviations. If any exclusions are made for these reasons, these exclusions will be described in the study report.

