9.3 Primary Efficacy Analysis Methods

The primary outcome for this study is a binary measure assessed at weeks 4, 8, and 12. A positive response is defined as a decrease from baseline of at least 10 points on the CAPS-5 score (Schnurr et al., 2022) and a reduction of at least 1 risk level of alcohol use, as defined by WHO (Knox et al. 2018). The treatment effect on comorbid PTSD + AUD over time will be assessed using a mixed logistic regression model. The model will be used to generate point and interval estimates of the risk differences and to test differences in proportions of PTSD+AUD resolution between treatment groups at the 8-week visit (primary timepoint), as well as at weeks 4 and 12 (secondary timepoints). The model will include fixed effects for the treatment group, visit (as a categorical variable), gender, site, presence/absence of anti-depressants, treatment-by-visit interaction, and random effects for participant (see model statement below). This approach will provide consistent estimates and valid inferences under missing at random (MAR) data assumptions while accounting for correlation among multiple measures on the same participant. This mixed model will improve the power of the study and the precision of all estimates by allowing all available measures for an individual to be incorporated in the analysis, even if other timepoints are missing. Sensitivity analysis maybe considered by excluding participants that have a low or moderate WHO risk level at baseline. This model is further described below:

$$g(E(Y_{ij})) = \beta_0 + \beta_1 \text{Visit}_{ij} + \beta_2 \text{Site}_{ij} + \beta_3 \text{Treatment}_{ij} + \beta_4 \text{Gender}_{ij} + \beta_5 \text{Anti-depressant}_{ij} + \beta_6 (\text{Treatment} * \text{Visit})_i + s_i + \varepsilon_{ij}$$

Where $g(E(\cdot))$ indicates the identity link function on the expected value of Y , Y_{ij} is the j th measure of PTSD+AUD measurement in subject i , β_0 is the intercept, β_1 through β_6 are coefficients, s_i is a random subject effect and ε_{ij} is the residual error term.

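### The SAP 9.2 rule for incomplete drinking look-backs uses a one-standard-deviation cut with no centre, so it cannot be programmed uniquely and makes one record's use depend on other participants' completeness

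*SAP*

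**What the plan says.** SAP 9.2 takes both the WHO risk level and %HDD from 28 consecutive days of Timeline Follow-Back (TLFB) data. On timing it says: "Each derived outcome measure for a specific timepoint will be based on the baseline visit date". If the window is not fully captured, participant data are excluded when "the number of total days included in look-back period is less than one standard deviation of the entire population". The same sentence stands in the composite row and in the %HDD row, both under primary outcomes.

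The baseline window is unlikely to be short, because "The screening measurement uses a 90-day recall period". Later visits recall drinking since the last measurement, and Protocol 7.3.4 adds: "There is a visit window of +/- 7 days for follow-up visits".

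The composite also needs a CAPS-5 result. SAP 9.3: "A positive response is defined as a decrease from baseline of at least 10 points on the CAPS-5 score", together with a drop of at least one WHO level. Protocol 4.2.1 codes anything other than success on both components as failure. SAP 7.3 allows no imputation. SAP 5.1 keeps non-completers in every analysis for which they have data.

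On early exit, Protocol 7.3.6 says: "If a participant exits prior to Week 8, all procedures for Week 8 are completed". Protocol 5.4.2 says that the reason "for early termination is documented and all Week 12 procedures are conducted". On out-of-window assessments, SAP 7.9 says only: "If any exclusions are made for these reasons, these exclusions will be described in the study report".

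**The concern.** A standard deviation is a spread. It becomes a cut-off only when a centre is named, and none is. The sentence could mean fewer days than the SD itself, than the mean minus one SD, or than 28 minus one SD. It does not say at which visit the SD is taken, whether people with no captured days enter it, or whether a visit or a whole participant is removed.

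Two programmers could therefore build different Week 8 %HDD datasets from the same data, with the differences falling mainly on people who leave early. SAP 7.5 plans no masked review of outcome data, so nothing later in the plan forces the choice to be made before assignments are known.

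Naming a centre would not cure the rule. The threshold would still move with trial-wide completeness, so identical records could be used in one trial and discarded in another.

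**Working it through.** The plan attaches no figure to this rule, so there is none to reproduce. I sized it under stated assumptions.

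**Inputs.** N = 90 and about 30% attrition (Protocol 10.5, SAP 6), with 20% and 40% as a range. The Week 8 window is days 29 to 56, anchored to the baseline date. Assumed: exit day even over days 1 to 84, no TLFB after exit, completers have all 28 days.

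**Captured days.** For exit day e, captured days = min(max(e − 28, 0), 28). With attrition a, each exit day carries w = 90a/84 people.
- At 30%, w = 27/84 = 0.3214.
- No days: 28w = 9.0 people. 1 to 27 days: 27w = 8.7. All 28 days: F = 90 − 55w = 72.3.

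**Mean and SD.** The sum of 1 to 27 is 378 and the sum of their squares is 6930.
- Total days = 378w + 28F = 121.5 + 2025 = 2146.5.
- Total squared = 6930w + 784F = 2227.5 + 56700 = 58927.5.
- Zero-day people counted (n = 90): mean 2146.5/90 = 23.85; SD = √(654.75 − 23.85²) = 9.27.
- Zero-day people left out (n = 81): mean 26.50; SD = √(727.5 − 26.5²) = 5.02.

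**Cut in days, with partial windows dropped in brackets.** Dropped = w × the number of whole days from 1 up to just below the cut. For example, a cut of 14.6 drops 14 × 0.3214 = 4.5 people.

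| SD taken over | Attrition | Mean | SD | days < SD | days < mean − SD | days < 28 − SD |
|---|---|---|---|---|---|---|
| all 90 | 30% | 23.85 | 9.27 | 9.3 (2.9) | 14.6 (4.5) | 18.7 (5.8) |
| those with any days | 30% | 26.50 | 5.02 | 5.0 (1.6) | 21.5 (6.8) | 23.0 (7.1) |
| all 90 | 20% | 25.23 | 7.82 | 7.8 (1.5) | 17.4 (3.6) | 20.2 (4.3) |
| all 90 | 40% | 22.47 | 10.34 | 10.3 (4.3) | 12.1 (5.1) | 17.7 (7.3) |

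**Dependence on others.** Under mean minus SD with everyone counted, the cut falls from 17.4 to 14.6 to 12.1 days as attrition rises from 20% to 40%. The same 15-day record is excluded at 20% and kept at 30% and 40%. Worse overall completeness admits shorter records.

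**Composite.** With everyone counted at 30%, the literal and mean-minus-SD readings disagree on records of 10 to 14 days, that is exit days 38 to 42. This is 5 × 0.3214 = 1.6 people. None of those days lies in the Week 8 visit window (days 49 to 63), so a Week 8 CAPS-5 exists for them only if an earlier exit assessment is labelled Week 8. What follows depends on coding:
- Under the Protocol's failure coding, losing the WHO level can change the composite only if that CAPS-5 meets the required decrease.
- If SAP 9.2 is taken literally, any cut record leaves the composite analysis.

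**Fixed minimum, same model at 30%.** At least 21 days drops 20 × 0.3214 = 6.4 of 90. At least 14 days drops 13 × 0.3214 = 4.2.

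**Week 2.** SAP 9.3.2 lists %HDD at Week 2. A 28-day window ending on day 14 runs from day −13, so 14 of its 28 days precede treatment. The Week 6 and Week 10 windows (days 15 to 42 and 43 to 70) are wholly after baseline.

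**The case against.** The best defence is that the ambiguity is narrower than it looks. SAP 5.1 makes intention-to-treat the basis of the analyses and SAP 8.4 describes that population as the entire efficacy population, so counting zero-day people is the more natural reading. Excluding only records shorter than the SD itself is hard to credit as intent. The two plausible readings, mean minus SD and 28 minus SD, then differ by 5.8 − 4.5 = 1.3 people of 90. TLFB recall reaches back to the last measurement, and participants may stay for assessments after stopping medication, so many gaps would be filled later. All of this stands and limits the size. It does not supply the missing centre or remove the dependence on other participants.

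Three stronger readings are tempting and not supported:
- A reader might infer that about 5 of 90 %HDD records are in dispute (6.75 − 1.61 = 5.1). That figure needs zero-day people left out and the least plausible reading as comparator.
- A reader might infer that near-complete visits would be discarded. That needs almost no zero-day participants. With everyone counted, the highest cut over all three readings at 20% to 40% attrition is 20.2 days, so a 21-day record is always kept.
- A reader might infer a breach of intention-to-treat. Only removal of whole participants conflicts with SAP 5.1 and 6. A visit-level minimum is an ordinary evaluability rule, though it should be named as an exception.

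**Conclusion.** The point holds as a defect in a stated rule. SAP 9.2 cannot be programmed uniquely, and under any reading the use of one record depends on the completeness of others. With zero-day participants counted and 30% attrition, the choice of reading moves the cut between 9.3 and 18.7 days and the partial windows dropped between 2.9 and 5.8 of 90. These counts rest on assumed even exits and no TLFB after exit, and later recall would lower them. The wording gap is certain; its size is illustrative.

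The consequence is direct for %HDD, which comes only from TLFB. For the composite it is small and conditional. A reader might infer that the primary result is at serious risk; the documents do not support that. They do leave open whether a composite with a cut WHO level is missing or a failure, and that needs an answer. The rule should be fixed before unmasking.

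**What to change.** Before unmasking, replace the SD sentence in both rows of SAP 9.2 with a fixed, visit-level minimum. For example: derive the WHO level and 28-day %HDD from the available days if at least 21 of the 28 window days are reported; otherwise set that visit's TLFB-derived value to missing and keep the participant's other visits. The figure 21 is 28 minus the 7-day visit window, or three full weeks. In addition:

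- State whether a composite with a missing WHO level is missing or a failure, given Protocol 4.2.1 and SAP 7.3.
- Name the minimum as an exception in SAP 5.1.
- Show a lower minimum, such as 14 days, as a sensitivity analysis.
- In SAP 9.3.2, drop or separately define 28-day %HDD at Week 2 only, and keep Weeks 4, 6, 8, 10 and 12. The optional 14-day look-back there needs its own minimum.
- Separately, reconcile Protocol 5.4.2 with 7.3.6. The schedule has TLFB and CAPS-5 at both Week 8 and Week 12, so for this point only the visit label is at stake.

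The downside is that 21 days is a convention. In this model it drops 6.4 of 90, more than any of the three readings with zero-day people counted, and some visits will rest on fewer than 28 days. The cost is a few sentences of SAP text and one repeat run of the affected models, with no new data.
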